Patients are expected to be aggressively treated to minimize the likelihood and/or severity of side effects at the discretion of the Investigator (consultation with the Karyopharm Medical Monitor is strongly encouraged), particularly GI symptoms and hematopoietic toxicities as observed in KPT-9274 animal toxicology studies. Supportive care including anti-nausea/anti-emetic therapy, acid suppression (e.g., proton pump inhibitors [PPIs] ± H2-blockers), anti-diarrheal therapy, and other standard treatments may be administered as per institutional guidelines for symptomatic patients. For additional options, see NCCN Supportive Care Clinical Practice Guidelines in Oncology. Note: the use of PPIs is allowed in all patients, but the Investigator must consult with the Karyopharm Medical Monitor prior to their use in patients receiving niacin ER. Supportive care recommendations for events such as anemia, arthralgias, and myalgias include the following; (1) anemia: dose interruption, dose reduction, use of growth factors (i.e., erythropoietins), and transfusions; (2) arthralgia: non-steroidal anti-inflammatory drugs (NSAIDs), cyclooxygenase-2 (COX-2) inhibitors, acetaminophen, tramadol, and low-dose steroids; and (3) myalgia and flu-like illness: KPT-9274 dosing at night, acetaminophen (including pre-treatment with acetaminophen), NSAIDs, COX-2 inhibitors, and low-dose steroids. For patients in Part A, the addition of niacin ER (up to 2,000 mg daily dose, per label) is allowed after completion of the DLT period in cycle 1 (first 28 days) in an attempt to offset potential side effect (i.e. anemia, arthralgias, myalgias, etc.)

of KPT-9274. Consultation with the Karyopharm Medical Monitor is recommended for questions regarding these recommendations.

Prohibited Concomitant Medications:

The use of niacin or niacin-containing supplements (e.g., multivitamins and energy drinks) is not allowed in the KPT-9274 only cohorts in the Dose Escalation or Expansion Phases. However, for patients in these cohorts that have cleared DLT in cycle 1, niacin ER (up to 2,000 mg co-administered with KPT-9274) may be used as supportive care in an attempt to offset potential side effects (e.g. anemia, arthralgias, myalgias, etc.) of KPT-9274. Prior to initiating niacin ER, patient symptoms and laboratory values should be reviewed and discussed with the Medical Monitor for this study.

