2.1.2. Secondary Objectives

Parts A and B

Dose Escalation

- To define the preliminary evidence of anti-tumor activity of KPT-9274 alone (Part A) and with co-administration of niacin ER (Part B) in patients with advanced solid malignancies or NHL.

Dose Escalation and Dose Expansion

[figure not shown]
- To determine the pharmacokinetic (PK) profile of KPT-9274, including, but not limited to, maximum plasma concentration, time-to-peak plasma concentration, terminal half-life, and plasma clearance.

Part C

- To determine the preliminary evidence of anti-tumor activity of KPT-9274 + nivolumab in patients with melanoma.
- To characterize the PK of KPT-9274 when administered with nivolumab in patients with melanoma.

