Enrollment is estimated at 175 patients. However, the number of patients required for completion of study enrollment cannot be defined *a priori* since this depends on the number of patients needed for the dose escalations in Parts A and B. Assuming that 9 dose levels of KPT-9274 are evaluated during both Part A (KPT-9274 single agent) and Part B (KPT-9274 + niacin ER) of the Dose Escalation Phase and up to 65 additional patients are enrolled in the Dose Expansion Phase the total combined enrollment is estimated to be 175 patients. Each cohort in Parts A and B of the Escalation Phase will consist of 3 or 6 patients per cohort. The Dose Expansion Phase may include up to 65 additional patients (up to 45 patients in the KPT-9274 ± niacin ER cohort; if Dose Expansion is conducted with KPT-9274 + niacin ER then an optional cohort of up to 20 additional patients in the KPT-9274 single agent cohort).

The KPT-9274 ± niacin ER expansion cohort will consist of 4 groups of approximately 45 patients (please note that the composition of the expansion groups [e.g., number of patients with NAPRT1 positive vs NAPRT1 deficient tumors] may change based on the results from the escalation phase) including the following:

- I. NAPRT1 deficient tumor group, approximately 10 patients
- II. NAPRT1 positive tumor group, approximately 10 patients
- III. Either NAPRT1 deficient or positive tumor group, approximately 10 patients
- IV. IDH1 mutant tumor group, approximately 15 patients

An additional, optional KPT-9274 single agent expansion cohort will consist of < 20 patients with any tumor mutational status.

Patients will receive oral KPT-9274 three times a week every other day (Days 1, 3, 5, 8, 10, 12, 15, 17, 19, 22, 24, and 26) during each 28-day cycle. During Part B of the Dose Escalation Phase, patients will receive 500 mg up to 2,000 mg niacin ER co-administered with each dose of KPT-9274.

Patients in the Dose Expansion Phase may be treated with the RP2D of KPT-9274 ±niacin ER according to the same schedule administered in the Dose Escalation Phase of the study.

Further details on the Dose Escalation phase are provided in Section [6.2.5](#) and Section [6.2.6](#) and additional details on the Dose Expansion phase are provided in Section [6.2.7](#).

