6.2.6.3. Dose Decision Meeting or Teleconference

To implement dose escalation decisions, available toxicity information (including all AEs and all laboratory abnormalities regardless of DLT assessment) will be evaluated by the enrolling Investigators and Karyopharm study personnel during a dose decision meeting or teleconference. Decisions will be based on an evaluation of all relevant data available from all dose cohorts evaluated in the ongoing study including safety information, DLTs, all NCI CTCAE (Version 4.03), toxicity data during Cycle 1 and PK data (if available) from evaluable patients.

Drug administration at the next higher dose cohort may not proceed until the Investigator receives written confirmation from Karyopharm indicating that the results of the previous dose cohort were evaluated and that it is permissible to proceed to the next higher dose cohort.

Interim safety data will be examined on an ongoing basis to ensure patient safety and to comply with the clinical study dose escalation rules (see Section 9.8). In addition, Karyopharm will conduct regular safety meetings with investigators and other site staff where all AEs are shared across the study, and appropriate management of toxicities fully reviewed and, as needed, implemented.

6.2.7. Dose Schedule for Evaluation During the Dose Expansion Phase (Parts A and B)

After completion of the Dose Escalation Parts A and B, Dose Expansion in up to 65 additional patients with advanced solid malignancies and NHL may be conducted to further explore safety, tolerability and preliminary evidence of anti-tumor activity of the RP2D of KPT-9274 ± niacin ER. Note that preliminary clinical results may define the patient population (i.e., specific indications) selected for enrollment in the Dose Expansion Phase.

After declaring the RP2D for KPT-9274 single agent and KPT-9274 + niacin ER, based on the safety and tolerability results of the Dose Escalation Phase, a decision will be made whether expansion (4 groups, ~45 patients total) will be conducted at the RP2D of KPT-9274 single agent or at the RP2D of KPT-9274 + niacin ER. If the ~45 patient expansion is conducted at the RP2D of KPT-9274 + niacin ER, an optional expansion with < 20 patients at the RP2D of KPT-9274 single agent may also be initiated.

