6.9. Supportive Care, Contraception Requirements, and Concomitant Medications

6.9.1. Supportive Care

Patients are expected to be aggressively treated to minimize the likelihood and/or severity of side effects at the discretion of the Investigator (consultation with the Karyopharm Medical Monitor is strongly encouraged), including hematologic and musculoskeletal (arthralgias and myalgias) symptoms observed in humans.

Supportive care including anti-nausea/anti-emetic therapy, acid suppression (e.g., PPIs \pm H2 blockers), anti-diarrheal therapy, and other standard treatments may be administered as per institutional guidelines for symptomatic patients. For additional options, please see NCCN Supportive Care Clinical Practice Guidelines in Oncology. Note: the use of PPIs is allowed in all patients but the Investigator must consult with the Karyopharm Medical Monitor prior to their use in patients receiving niacin ER. If any deficiencies in vitamin B12, folate, iron, erythropoietin, or transferrin are observed, then standard medical practice for their replacement should be instituted.

Anemia appears to be dose dependent and should be treated with dose interruption, dose reduction, use of growth factors (i.e., erythropoietins), and/or transfusions. The addition of niacin ER (up to 2,000 mg daily dose, per label) will be allowed after completion of the DLT period in cycle 1 (first 28 days) in an attempt to offset potential side effect (i.e. anemia, arthralgias, myalgias, etc.) of KPT-9274. After Week 8, niacin may be titrated, as per label, to patient response and tolerance. If response to 1000 mg daily is inadequate, increase dose to 1500 mg daily; may subsequently increase dose to 2000 mg daily. Daily dose should not be increased more than 500 mg in a 4-week period, and doses above 2000 mg daily are not recommended. Women may respond at lower doses than men.

Arthralgia should be treated with non-steroidal anti-inflammatory drug (NSAIDs), cyclooxygenase-2 (COX-2) inhibitors, acetaminophen, tramadol, and/or low-dose steroids. Myalgia and flu-like illness should be treated with KPT-9274 dosing at night, acetaminophen (including pre-treatment with acetaminophen), NSAIDs, COX-2 inhibitors, and/or low-dose steroids. Consultation with the Karyopharm Medical Monitor is recommended for questions regarding these recommendations.

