6.9.3. Prohibited Concomitant Medications

The use of niacin or niacin-containing supplements (e.g., multivitamins and energy drinks) is not allowed in cycle 1 of the Part A KPT-9274 only cohorts in the Dose Escalation or Expansion Phases. However, for patients in these cohorts that have cleared DLT in cycle 1, niacin ER (up to 2,000 mg co-administered with KPT-9274) may be used as supportive care in an attempt to

offset potential side effects (e.g. anemia, arthralgias, myalgias, etc.) of KPT-9274. Prior to initiating niacin ER, patient symptoms and laboratory values should be reviewed and discussed with the Medical Monitor for this study.

Investigational or commercial anticancer agents other than KPT-9274 are not allowed during the study. The initiation of any non-protocol specific anti-tumor treatment is considered an indication of disease relapse/progression and should be recorded appropriately in the eCRFs.

There are exceptions including localized palliative radiation (see Section [6.9.2.3](#)), hormonal contraception for the prevention of pregnancy (see Section [6.9.2.2](#)), hormonal therapy for patients with prostate cancer (see [Section 6.9.2.4](#)), and blood products/growth factors (see [Section 6.9.2.6](#)). For other possible cases, please consult the Karyopharm Medical Monitor.

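### Patients in the KPT-9274-only cohorts may add niacin ER after Cycle 1, and neither document splits or flags their outcomes when they do

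*Protocol*

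**What the plan says.** **The allowance.** In Protocol Section 6.9.3, niacin "is not allowed in cycle 1 of the Part A KPT-9274 only cohorts in the Dose Escalation or Expansion Phases". Once a patient has cleared the DLT period, "niacin ER (up to 2,000 mg co-administered with KPT-9274) may be used as supportive care". Section 6.9.1 agrees that the addition "will be allowed after completion of the DLT period in cycle 1", and the synopsis (Supportive Care) says for Part A that "the addition of niacin ER (up to 2,000 mg daily dose, per label) is allowed after completion of the DLT period in cycle 1". The stated reason is to offset side effects such as anemia, arthralgia and myalgia, and Section 6.9.3 asks for prior discussion with the Medical Monitor.

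**The Part B regimen.** Under Section 3.1, Part B "patients will receive 500 mg up to 2,000 mg niacin ER co-administered with each dose of" KPT-9274.

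**What Part A is meant to show.** The secondary objective in Section 2.1.2 concerns "anti-tumor activity of KPT-9274 alone (Part A) and with co-administration of niacin ER (Part B"). Under Section 6.2.7, based on escalation safety and tolerability, "a decision will be made whether expansion (4 groups, ~45 patients total) will be conducted at the RP2D of KPT-9274 single agent" or with niacin. The same section carries Part A patients treated at the chosen RP2D into the expansion analyses.

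**How results are grouped.** Protocol Section 9.1 presents efficacy and safety separately by part. SAP Section 5 presents safety by part and cohort. The SAP's primary efficacy population (Section 3.1.1) is every treated patient. Tables 4-2 and 4-3 list new antineoplastic therapy as the only treatment change that censors. SAP Section 2.8 plans no subgroup analysis.

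**The concern.** From Cycle 2 a patient in a KPT-9274-only cohort may be taking a combination that overlaps Part B, yet everything that patient contributes is still reported under Part A. No sentence says so outright; it follows from grouping by part with no rule that reassigns, censors, splits or flags at niacin start.

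Niacin is not a neutral supportive drug here. Protocol Section 1.3.2 introduces it to reduce side effects, and Section 1.2 says niacin can bypass NAMPT inhibition where NAPRT1 is expressed. It could therefore alter both tolerability and activity. It is also started in response to toxicity, so its use depends on outcome.

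At stake is how single-agent KPT-9274 is described after Cycle 1: later adverse events, response, disease control, PFS and TTP, and the patients who count toward the single-agent futility rule in Section 9.5.1.

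**Working it through.** **1. The plan's own figure, and why it is untouched.** Protocol Section 9.8 gives 0.57 as the probability of halting at a cohort when the true DLT rate is 33%. Under the 3+3 rule of Section 6.2.6.1, escalation occurs on 0/3, or on 1/3 followed by 0/3.

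- P(0/3) = 0.67³ = 0.3008; P(1/3) = 3 × 0.33 × 0.67² = 0.4444.
- P(halt) = 1 − (0.3008 + 0.4444 × 0.3008) = 0.566. With p = 1/3 it is 0.572.

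The figure reproduces. It uses Cycle 1 DLTs only, and niacin is barred in Cycle 1, so dose escalation and the MTD are unaffected.

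**2. Timing.**

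- Earliest niacin: the day after the 28-day DLT period, Day 29.
- First eight-weekly scan: Day 1 of Cycle 3, which is Day 57 (Protocol Sections 7.3.2.1 and 7.3.3.1; SAP Section 2.7), with a window of ± 7 days. Earliest 57 − 7 = Day 50.
- Gap: 50 − 29 = 21 days. Every scheduled eight-weekly scan is at least three weeks after niacin becomes permissible.
- Stable disease of at least 16 weeks: 16 × 7 = 112 days, of which 112 − 28 = 84, or 75%, fall in the permitted period.
- Futility: Section 9.5.1, the synopsis and the SAP use about 16 weeks, but Section 6.2.7 uses about 8. On the 8-week reading the share is (56 − 28)/56 = 50%. Those passages must be reconciled.

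**3. What the analysis rules do with niacin.**

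| SAP item | What it shows | Splits or flags outcomes at niacin start? |
|---|---|---|
| Section 3.4, exposure by drug | Niacin duration and dose | No |
| Section 3.3.1, concomitant medications | Who took what | No |
| Section 5.1.2, causality categories | Attribution, including to niacin only | No |
| Tables 4-2 and 4-3, censoring | New antineoplastic therapy | No; niacin is not listed |
| Section 5, safety grouping | Part and cohort | No |

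**4. Could the effect on futility be signed?** The documents give no disease-control rate for either regimen, so the rates here are assumptions. Let a be the rate alone, b the rate with niacin and s the share adding niacin, and suppose those patients take on rate b in full. Then p = (1 − s)a + sb, and the chance of at least one success in ten is 1 − (1 − p)¹⁰.

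| s | p if a = 5%, b = 20% | Pass | p if a = 20%, b = 5% | Pass |
|---|---|---|---|---|
| 0 | 5% | 0.40 | 20% | 0.89 |
| 0.25 | 8.8% | 0.60 | 16.3% | 0.83 |
| 0.50 | 12.5% | 0.74 | 12.5% | 0.74 |
| 0.75 | 16.3% | 0.83 | 8.8% | 0.60 |

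The sign follows the assumption. The table shows that the futility count can be sensitive to niacin use; it estimates nothing about this trial.

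**The case against.** Four objections carry weight.

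- **The toxicity that prompts niacin is already counted.** It arose on KPT-9274 alone, and SAP Sections 5.1.2 and 5.1.3 count each event once per patient and tabulate maximum grade. A reader might infer that niacin hides single-agent toxicity. The documents support that only for later worsening and for new kinds of event.
- **Mixing is permitted, not shown.** A reader might take the 23 Part A patients in Table 10 (3 + 3 + 5 + 7 + 5, of 47) as the number affected. That is only an upper bound at that data cut: Appendix 6 lists the allowance as added in Version 4.1, dated 13 December 2017, so earlier patients may never have had the option, and actual use is not reported. Nor is all activity information exposed. Patients who never start niacin, deaths or progressions in Cycle 1, and end-of-treatment scans after very early discontinuation are free of niacin.
- **There is no planned A-versus-B contrast.** The study is uncontrolled, adverse event rates are not tested (Section 9.8.1), and Table 10 shows 10–40 mg in Part A against 30–100 mg in Part B. A reader might want to calculate how far niacin use shrinks an A-minus-B difference. That contrast would be confounded by dose anyway, and the documents supply no rates for it.
- **Reporting by assigned part is legitimate.** Niacin is permitted supportive care alongside transfusions and growth factors. The exposure, medication and causality displays, with the by-patient listings promised in Protocol Section 9.4, go some way toward identifying users.

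On activity, escalation enrolls NAPRT1-negative to NAPRT1-positive patients 2:1, and Section 1.3.2 says tumors lacking NAPRT1 function may be unable to use niacin. Any loss of activity would then mainly concern the planned minority, while better tolerability could keep patients on drug longer. The direction is open.

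What survives is narrow: none of the displays links niacin use to the outcome it may have changed.

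**Conclusion.** The gap is real and limited. Following the plan, data collected after niacin start would be reported as KPT-9274 alone with nothing to mark them. DLT, MTD and other Cycle 1 results are clean. All scheduled eight-weekly response scans and 84 of the 112 days behind 16-week disease control fall when niacin is permitted. The single-agent results, the single-agent futility count and the Part A patients carried into expansion may therefore include niacin-treated time.

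The size of any distortion cannot be derived from the documents, because they give neither the number of users nor the effect of niacin on these endpoints. The conclusion rests on two readings: that Part A patients stay in Part A for analysis, which the grouping implies, and that no separate plan handles the matter. It does not show that single-agent results are wrong, that toxicity is concealed, or that dose finding is compromised. It is a cheap improvement to what the trial can say about the single agent.

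**What to change.** Keep the by-part analysis as primary and add to the SAP:

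1. The number of Part A and single-agent expansion patients who started niacin, and the study day of first dose.
2. Adverse events in these cohorts by treatment at onset, before or after first niacin dose, with exposure time for each period and a stated rule for same-day onsets. A footnote should say that the later column contains only patients who cleared Cycle 1.
3. Niacin use and start date as a flag in the listings of responders, patients with stable disease of at least 16 weeks, and patients counted for futility.
4. A sensitivity analysis of PFS, TTP and duration of disease control censored at first niacin dose, labelled as subject to informative censoring because niacin is started for toxicity. Two details need stating. First, moving censoring back to the last assessment, as Tables 4-2 and 4-3 do, would place anyone starting niacin before the first scan at Day 1. Second, SAP Section 1.3.1 starts duration of disease control at first treatment, but Table 4-1 starts it when the criteria are first met, which may be after niacin began.

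The niacin wording also needs reconciling: the synopsis and Section 6.9.3 phrase the ban differently, and Sections 6.9.1 and 6.9.2.1 do not confine the allowance to Part A. No view is taken on which rule should apply.

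The cost is programming. Concomitant medications and changes are recorded on the eCRF (Protocol Section 7.5.1.5), and SAP Section 2.2.2 already handles partial medication dates. The downsides are small cells and possible informative censoring.

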7. ASSESSMENTS

7.1. Informed Consent

Study-specific assessments may not be performed until the patient provides written informed consent (see Section 10.4).

7.2. Demographic and Baseline Characteristics Assessments

7.2.1. Demographics

Patient demographics (including date of birth, sex, race, ethnicity, and age at time of consent) will be collected at study entry.

7.2.2. Medical History

A complete medical history will be obtained from each patient. Medical history will include baseline symptoms of the disease under study as well as a detailed history of prior procedures for the patient's NHL or advanced solid malignancy and other prior cancer therapies (i.e., chemotherapy, hormonal therapy, immunotherapy, biotherapy, radiotherapy, and surgery), including start and end dates, best response, disease progression during or after therapy, as well as discontinuations due to intolerance, toxicity, or any other serious illness; Tumor Nodes Metastasis (TMN) staging will be collected on for patients with advanced solid malignancies. Smoking history will be recorded. A detailed history of disease-specific diagnostic and prognostic testing and test results (such as phenotypic and cytogenetic profiles) will also be collected.

7.2.3. Disease Risk Assessment (NHL patients only)

Disease risk assessment will be performed according to the Revised International Prognostic Index (R-IPI; [Sehn, 2007](#)) for NHL patients only.

7.2.4. Baseline Characteristics and Determination of Eligibility

Baseline characteristics will include ECOG performance status, duration from initial diagnosis, response to previous therapy, types of prior therapy, and height/weight.

Inclusion/exclusion criteria will be reviewed to determine eligibility.

Patients with known active HAV, HBV, HBC, or HIV infection will be excluded from this study. However, testing for these viruses is not required as part of this study.

7.2.5. Determination of NAPRT1 and IDH1 Tumor Status

NAPRT1 and IDH1 tumor status for Parts A and B must be determined prior to enrollment in the KPT-9274 ± niacin ER escalation and expansion cohorts. Archival biopsy material obtained \leq 6 months prior to screening may be used to prescreen patients for NAPRT1 and IDH1 tumor status. A fresh biopsy will be collected during screening to determine or confirm that NAPRT1 and IDH1 tumor status. Screening period includes Day -30 to Day 7 prior to C1D1. Additional details are provided in Section 7.4.3.3.

7.2.6. Determination of Patients with Melanoma Who Progressed on Prior Anti-PD-1 or Anti-PD-L1 Treatment

Patients with melanoma who progressed on prior anti-PD-1 or anti-PD-L1 treatment must be determined prior to enrollment in Part C - KPT-9274 + nivolumab. Screening period includes Day -30 to Day -1 prior to C1D1.

